protocol. The stepped wedge design randomizes level I trauma center sites to sequentially initiate the intervention, thus allowing within site pre-, post- intervention comparisons, as well as between site comparisons. An additional advantage of the stepped wedge design for the UH3 protocol is that it would be impractical to roll out the entire intervention at 24 sites simultaneously. Finally, from an implementation science perspective there is an advantage to having the intervention ongoing at the end of the study at every site, should the intervention demonstrate a significant impact on PTSD and comorbidity. Given that there is little threat of contamination at each site across intervention and control patients and that the UH3 can accommodate the increased potential length of active recruitment and follow-up, the stepped wedge design appears to be an optimal choice for the UH3 protocol. In the proposed UH3 protocol stepped wedge design, all 24 participating level I trauma centers are randomly assigned to 1 of four waves. Each wave is assigned a specific proportion of control and intervention patient recruitment. Wave 1 recruits 8 control and 32 intervention patients, wave 2 recruits 16 control and 24 intervention, wave 3 recruits 24 control and 16 intervention and wave 4 recruits 32 control and 8 intervention patients. Interventions are initiated in the second six months of the UH3. The proposed stepped wedge design is outlined in the figure below.

Figure 16. Stepped Wedge Cluster Randomized Design

The stepped wedge regression model will adapt the functional form given below, and uses a timedependent variable to code treatment status for cluster *k* at calendar time *t*, denoted as condition_{kt.} For the stepped wedge study design there are now two key time scales: Period, which denotes the study period measured relative to the calendar time when the overall study begins; and Follow-up time which is a patientspecific time scale relative to when they enrolled in the study. In this model mean outcomes may have a temporal trend in calendar time and this will be captured by modeling "Period", while the primary outcome will still be the 12-month patient outcome denoted by Y_{ijkt} where i=4.

A) The primary analysis regression model will adapt the functional form given below:

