 $Y_{4jkt} = \beta_0 + \beta_1^* \text{Period}_{4jk1} + \beta_2^* \text{Period}_{4jk2} + \beta_3^* \text{Period}_{4jk3} + \beta_4^* \text{Period}_{4jk4} + \beta_5^* Y_{1jkt} + \beta_6^* \text{condition}_{kt} + \text{Mean model}$

Trauma center random effect and error

 $b_{k,0} + e_{4jkt}$

For this analysis the null hypothesis of no intervention effect is captured by H_0 : $\beta_6=0$, and the primary statistical test will be a Wald test of this null hypothesis.

B) A secondary analysis will explore the potential for treatment effect heterogeneity at the center level through inclusion of an additional random effect that permits cluster-specific variability in the intervention impact, captured by a random coefficient on the time-varying condition covariate:

 $Y_{4jkt} = \beta_0 + \beta_1 * \text{Period}_{4jk1} + \beta_2 * \text{Period}_{4jk2} + \beta_3 * \text{Period}_{4jk3} + \beta_4 * \text{Period}_{4jk4} + \beta_5 * Y_{1jkt} + \beta_6 * \text{condition}_{kt} + \text{Mean model}$

 $b_{k,0} + b_{k,1}$ *condition_{kt} + e_{4jkt}

Trauma center random intercept, slope, and error

The key difference for this model is that the intervention effect at trauma center k would be allowed to vary across centers and would involve the overall average intervention effect and a center-specific random intervention effect: β_6 + $b_{k,1}$. For this analysis the null hypothesis of a null average intervention effect is still captured by H₀: β_6 =0, and the primary test will be a Wald test of this null hypothesis, but now using an additional random intervention effect together with a standard random trauma center effect (random intercept).

C) A secondary analysis will evaluate the impact of intervention at all of the longitudinal follow-up times by including additional outcome measures and associated follow-up time variables, and interactions between follow-up time and intervention:

$$\begin{split} Y_{ijkt} &= \beta_0 + \beta_1 * \text{Period}_{ijk1} + \beta_2 * \text{Period}_{ijk2} + \beta_3 * \text{Period}_{ijk3} + \beta_4 * \text{Period}_{ijk4} + \beta_5 * \text{Followup}_{2jkt} + \beta_6 * \text{Followup}_{3jkt} + \\ \beta_7 * \text{Followup}_{4jkt} + \beta_8 * \text{condition}_{kt} + \beta_9 * \text{Followup}_{2jkt} * \text{condition}_{kt} + \beta_{10} * \text{Followup}_{3jkt} * \text{condition}_{kt} + \\ \beta_{11} * \text{Followup}_{4jkt} * \text{condition}_{kt} + \\ \end{split}$$

Mean model

a _{jk,0} + a _{jk,1} *Followup _{ijkt} +	Patient random effects

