$b_{k,0} + b_{k,1}$ *condition _{kt} + e_{ijkt}	Trauma center random effects and error

Y_{ijkt} denotes patient outcome at follow up time i (i=1,2,3,4) (baseline, 3m, 6m, 12m)

for patient j ($j=1,2,...,n_k$)

at trauma center k (k=1,2,...,24)

enrolled in time period t (t=0,1,2,3,4)

For secondary analysis using the repeated measurements from each subject there are two key hypotheses to test. First, the 12-month intervention effect would now be captured by the intervention-by-time interaction specific to the 12-month assessment time: H_0 : β_{11} =0; and evaluation of the intervention effect under this model evaluates any impact of using the partially complete longitudinal data for all subjects to estimate the 12-month intervention effect. This analysis provides a sensitivity analysis evaluating the impact of missing 12-month data for subjects who do have partial follow-up data (e.g. 3 month, 6 month data). A second exploratory hypothesis would be the global null of no intervention effect at all follow-up times, and this would be captured by the multivariate null hypothesis: H_0 : $\beta_8 = \beta_9 = \beta_{10} = \beta_{11} = 0$; and evaluated using a multivariate Wald test. Under this hypothesis the intervention and control means within a given period would be equivalent for all patient follow-up times.

The primary analysis is a single hypothesis test based on Model (A) and will use alpha=0.05. All other statistical tests are conducted to evaluate the sensitivity of the primary analysis to either heterogeneity or missing data, and therefore multiple comparison corrections are not used for these secondary analyses.

Subject Attrition: Some attrition is expected in the study sample due to the research context and the population under study (i.e., low income, ethnoculturally diverse, injured trauma survivors). Prior studies by the

investigative group have consistently achieved follow-up completion rates \geq 75-80% at 12 months post-injury with this population. Estimates derived from these rates are incorporated into the descriptions of subject flow and power analyses.

4. Sample size and power

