A number of issues specific to the design and analyses of cluster randomized trials are addressed by the current power analyses.²⁹⁸⁻³⁰² A key consideration for the trial is the nesting of patients within trauma center sites and the ascertainment of associated intraclass correlations (ICC). The study team has extensive experience with prior multisite trauma center observational and pragmatic clinical trial investigations. Sample size estimates were therefore adjusted for the clustering of patients within trauma center sites, using appropriate ICCs derived from the study team's prior multisite investigations; original ICCs utilized included, PTSD Checklist ICC = 0.0083, PHQ-9 ICC = 0.0259, AUDIT ICC = 0.0059, SF-36 PCS ICC = 0.003.Original sample size estimates suggested recruiting 20 trauma center sites with a total study N = 800 patients (n = 40 patients per site).

Table 10. PTSD Checklist Effect Sizes					
	Intraclass Correlation				
PTSD Checklist	0.005	0.010	0.020	0.030	
Minimum Detectable Effect Size	0.216	0.220	0.227	0.231	

In response to a series of discussions with the NIH Health Care Systems Biostatistics Core, sample size estimates were revised using more conservative ICCs. The power analyses model the baseline to 12-month treatment effect for the primary outcome and secondary outcomes. Table 10, provides effect sizes for the PTSD Checklist with a range of ICCs that includes empirically derived ICCs from the investigative team's prior studies as well more conservative ICC estimates suggested by the NIH Health Care Systems Collaboratory Biostatistics Core. Table 11 delineates the parameters used to estimate power for the PTSD Checklist, PHQ-9, AUDIT, and SF-PCS. Sample size estimates were derived using the STATA statistical package.³⁰³ With each of the 24 trauma center sites recruiting 40 patients into the study, the study has 80% power to detect effect sizes ranging from 0.22 to 0.23. These effect sizes are smaller than our previously observed treatment effect for PTSD symptoms of 0.34. In prior investigations PTSD treatment effects of 0.34 have been associated with clinically significant and policy relevant functional outcome improvements.

Table 11. Stepped Wedge Power for UH3 Outcomes					
Continuous outcomes	PTSD Checklist	PHQ9	AUDIT	SF-36 PCS	
Cluster size at baseline	40	40	40	40	
Cluster size estimation at 12m (25%	30	30	30	30	
attrition)					
Total Number of clusters	24	24	24	24	
alpha	0.05	0.05	0.05	0.05	
Power	0.8	0.8	0.8	0.8	

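### Model C's site effects cancel out of its 3-, 6- and 12-month tests, so those intervals are too narrow if sites differ in recovery or in intervention effect

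*Combined protocol and SAP*

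**What the plan says.** In the Statistical Analysis Plan, item 3 (Stepped wedge cluster randomized design), Models A and B take only the 12-month score as outcome, with the baseline score as a covariate. Model A has a random site intercept. Model B adds b_k,1 × condition_kt, described as "inclusion of an additional random effect that permits cluster-specific variability in the intervention impact".

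Model C takes all four assessments as outcomes, with i = 1 for baseline and i = 2, 3, 4 for 3, 6 and 12 months. Its site line, labelled "Trauma center random effects and error", is b_k,0 + b_k,1 × condition_kt + e_ijkt. Condition is indexed by site and enrolment period, not by visit. The only random term that multiplies Followup is the patient-level a_jk,1. For the test, "the 12-month intervention effect would now be captured by the intervention-by-time interaction specific to the 12-month assessment time", with H0: β11 = 0.

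The plan presents this test as a sensitivity analysis for missing 12-month data. It is explicit about the hierarchy: "The primary analysis is a single hypothesis test based on Model (A) and will use alpha=0.05". No robust variance is named for Model C; clustered bootstrapping appears only in the cost analyses.

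**The concern.** β11 is the difference between conditions in change from baseline to 12 months, and β9 and β10 are the same contrast at 3 and 6 months. A site term that adds the same amount at baseline and at follow-up cannot affect a contrast in change. The term that Model B uses for site variation in the intervention effect therefore does another job in Model C: it lets the baseline difference between control-phase and intervention-phase enrolees vary by site. Nothing in Model C lets recovery, or the effect on recovery, differ between the 24 sites.

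Such differences are plausible on the protocol's own description. Delivery of intervention elements depends on the care manager's available time, supervision ranges from one to four calls a month, and sites have roughly one to five care managers. If sites do differ, the standard errors of β9 to β11 are too small. A reader comparing Model C with Model A would then see a check on the primary result with an error bar that leaves out part of the uncertainty. Model C is also the only written equation for the 3- and 6-month effects, and the analytic approach is to be repeated for the secondary outcomes.

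**Working it through.** **1. Inputs, and the plan's own figure.** Item 4 (Sample size and power) plans for 40 patients at each of 24 sites, 24 × 40 = 960 in all, and on that basis claims that "the study has 80% power to detect effect sizes ranging from 0.22 to 0.23". Table 11 takes ICC 0.02, autocorrelation 0.7 and 25% attrition (40 to 30 per site). On allocation, "Wave 1 recruits 8 control and 32 intervention patients, wave 2 recruits 16 control and 24 intervention"; waves 3 and 4 mirror this at 24/16 and 32/8. That implies five periods of 8 patients per site, or 6 per site-period at 12 months. Sidedness is not stated; two-sided 0.05 is assumed.

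The standard stepped-wedge variance with fixed period effects, times the ANCOVA factor √(1 − 0.7²) = 0.714, gives detectable effects of 0.2161, 0.2203, 0.2267 and 0.2311 at ICC 0.005, 0.010, 0.020 and 0.030. Table 10 has 0.216, 0.220, 0.227 and 0.231. The inputs are therefore read correctly.

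**2. Cancellation.** For a patient seen at both visits, Model C gives

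Y_4jkt − Y_1jkt = β7 + β11 × condition_kt + a_jk,1 × (change in Followup) + (e_4 − e_1).

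Neither b_k,0 nor b_k,1 remains. A generalised least squares check used Model C as written, 75% seen at 12 months, and assumed variances of 0.28 residual, 0.68 patient intercept, 0.04 patient slope and 0.02 site. The SE of β11 stays at 0.055810 as Var(b_k,1) goes from 0 to 0.25 and as Var(b_k,0) goes from 0 to 0.10. Over the same range of Var(b_k,1) the SE of β8, the baseline contrast, rises from 0.094 to 0.142.

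**3. What is left out.** Work in outcome SD units. With complete pairs and no Period-by-visit terms, β11 is the difference in mean change. Each condition enrols 6 × (8 + 16 + 24 + 32) = 480, of whom 0.75 × 480 = 360 are seen at 12 months.

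- Patient variance: 2 × (1 − 0.7) × (2/360) = 0.6 × 0.005556 = 0.00333. This is all that Model C counts.
- Site variance of change, σs²: a site's weight is its share of intervention patients minus its share of control patients, ±24/480 in waves 1 and 4 and ±8/480 in waves 2 and 3. Sum of squares: 6 × 2 × (0.05² + 0.01667²) = 0.0333.
- Site variance of the effect, τ²: 6 × (32² + 24² + 16² + 8²)/480² = 6 × 1920/230400 = 0.05.

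SE factor = √[(0.00333 + 0.0333σs² + 0.05τ²)/0.00333]; type I error = 2 × [1 − Φ(1.96/factor)].

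| Assumed σs² | Assumed τ | SE factor | Type I error |
|---|---|---|---|
| 0 | 0 | 1.00 | 5.0% |
| 0.005 | 0 | 1.02 | 5.6% |
| 0.0083 | 0 | 1.04 | 6.0% |
| 0.02 | 0 | 1.10 | 7.4% |
| 0 | 0.10 | 1.07 | 6.8% |
| 0 | 0.15 | 1.16 | 9.0% |
| 0.02 | 0.10 | 1.16 | 9.2% |
| 0.02 | 0.15 | 1.24 | 11.4% |

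The values 0.0083 and 0.02 are the team's earlier PTSD Checklist ICC and the planning ICC, used here as if all of that variance were variance of change. The values of τ are assumptions; with the Table 11 SD of 15 they equal 1.5 and 2.25 points.

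**4. Cross-check.** Fitting Model C at its best-fitting variance components, with the variances in step 2, gives 7.1% for a site SD of change of 0.14 (variance 0.02), 6.8% and 9.0% for τ of 0.10 and 0.15 alone, and 11.0% for 0.14 with τ = 0.15. With no site variation in change, coverage is 95.0%.

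A REML simulation of 700 trials with σs² = 0.02 and τ = 0 rejected in 6.3% (95% CI about 4.6-8.3%). That is compatible both with 5% and with the predicted 7.4%, so it settles nothing; the case rests on the algebra and the least squares check.

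**The case against.** The strongest reply is about size. A reader might infer that Model C's intervals are too narrow as a matter of fact. The documents do not support that: they give no between-site variance of change or of effect, and at zero the interval is correct. The 7.4% figure puts the whole of a deliberately conservative ICC into change. If site effects correlated 0.7 between baseline and 12 months (an assumption), σs² would be 2 × 0.3 × 0.02 = 0.012, giving 6.4%; the same step from 0.0083 gives 5.6%. This stands, and it is why the size is shown as a range.

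A reader might also infer that the primary result is at risk, or that Model C could rescue it. Model A has no baseline outcome row and is unaffected, and no rule in the plan lets Model C override it. Site variation in effect is assigned to Model B, where b_k,1 works as intended. This stands too.

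Last, the plan presents its equations as forms to be adapted, and its general text says that mixed models accommodate centre heterogeneity. That leaves room to add a term. But Model C's random effects and tested coefficient are written out, and an analyst who follows them omits site variation in change.

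**Conclusion.** The gap is real and is confined to a secondary model. As written, the tests of β9, β10 and β11 contain no site clustering of change, and the global test that includes them inherits this. The cancellation is exact and needs no assumption. The consequence does need one: sites must differ in recovery or in intervention effect. Under the values assumed here, a nominal 5% test runs at about 6.0-7.4% from site variance of change alone, 6.8-9.0% from effect heterogeneity alone, and 9-11% from both with σs² at 0.02. These figures assume r = 0.7, 25% attrition, a two-sided test, and a mean model without Period-by-visit terms. The correction is worth making before analysis because it is cheap and because Model C will be read as a check on the primary result.

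**What to change.** Write the site line of Model C as

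b_k,0 + b_k,1 × condition_kt + b_k,2 × post_i + b_k,3 × condition_kt × post_i + e_ijkt,

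with post_i = 0 at baseline and 1 at 3, 6 and 12 months. Then b_k,2 carries site differences in recovery and b_k,3 carries site differences in the intervention effect. Keep b_k,1 rather than moving it onto post_i, because it protects β8, which is part of the stated global test. Without it, an assumed site SD of 0.15-0.20 in the baseline difference makes the SE of β8 too small by a factor of 1.07-1.12 (type I error 6.6-7.9%). The alternative is a cluster-robust variance with a small-sample correction for 24 sites, which also avoids assuming the same site deviation at all three follow-up visits.

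The cost is one line of the plan, wider intervals for β9 to β11, and two more variance components to estimate from 24 sites. With variance components taken as known, modelling site effects on change leaves the SE of β11 at 0.0558 when sites do not differ. It raises the SE from 0.0560 to 0.0600 (+7%) at τ = 0.10 and from 0.0563 to 0.0646 (+15%) at τ = 0.15. The intervals may be slightly conservative: in the simulation, a variant with site terms acting only after baseline rejected in 3.3% of trials (95% CI 2.1-4.9%).

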Phase 4: Control phase initiation. Sites will be trained in the study protocol, recruitment procedure, consent process, and how to use the decision support tool recruitment modules. Recruitment of control patient subjects will begin following this training. Data quality assessment procedures and baseline standardized patient interviews with care manager provider subjects will also occur in this phase.

Phase 5: Follow-up outcome assessments. Follow-up interviewer training will begin prior to the initiation of this phase. The 3-, 6- and 12-month, blinded follow-up interviews will begin and continue ongoing throughout this phase.

Phase 6: Intervention phase initiation. Recruitment of control patient subjects will end at each site based upon the wave they are assigned in the stepped wedge design. The UW intervention study team members will conduct a one-day intervention training workshop at each site at this time. Following this training, each site begins recruitment of intervention patient subjects and their care manager subjects begin charting notes in the decision support tool and have regular supervision with the UW study team. Intervention feedback and coaching will occur during this phase. Standardized patient sessions continue during this phase. Data quality assessment procedures will also continue at each site in this phase. All provider subjects will be asked to complete another organizational survey, after this phase is completed.

Phase 7: Final study procedures. Final data cleaning and analyses will be conducted in this phase. Manuscript preparation and the end of study policy summit will occur in this phase. The UW study team will coordinate with the American College of Surgeons' Committee on Trauma, as well as other stakeholders to hold a policy summit.

C. Site Eligibility and Recruitment

Over the course of the start-up phase, the TSOS study team has recruited the 24 trauma center sites that will

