Patient identification and recruitment procedures described below were successfully piloted during the the UH2 start-up phase of the project. PTSD interventionist and other providers will identify potential patient subjects by reviewing inpatient rosters and identifying individuals who are most likely to have PTSD using the UW study team's validated PTSD screening algorithm further described below. Care manager subjects will then approach potential patient subjects about the study.

1. Potential patient subjects are identified by searching health records at each site for inpatients brought into the hospital for a traumatic injury. In order to review those records for this purpose, the study team will apply for and receive a waiver of consent and a waiver of HIPAA authorization.

2. In order to enhance the efficiency of trauma care system PTSD case finding, the study team has developed and implemented a 10 domain PTSD risk factor screen (Appendix 5).⁴⁹ The 10 domains used for screening are: 1) Female gender, 2) Non-white race/ethnicity, 3) Intentional injury, 4) Public or Veterans insurance status, 5) Intensive Care Unit (ICU) admission, 6) Previous hospitalizations 7) Substance use, 8) Tobacco use, 9) Evidence of PTSD diagnosis, 10) Other mental health diagnosis.

3. The PTSD screening evaluation can either be applied in an automated or manual format. The automated form of the evaluation can be programmed into the hospital computing system, while the manual form of the evaluation involves screening individual health records for the 10 PTSD risk factor domains. At both automated and manual sites that select the manual screening, UW study team members will train PTSD intervention care manager subjects to adhere to the chart abstraction checklists developed and validated by the UW study team (see also the Data Quality Assurance and Harmonization section).

4. Each day the PTSD interventionist will oversee a hospital-based review for admitted injured patients. The review will aggregate data from the 10 PTSD risk factor domains. Patients with higher scores on the evaluation (i.e., more positive risk elements) will be prioritized for approach for formal PTSD symptom assessment with the PTSD Checklist. Providers will identify potential patient subjects who meet the criteria of

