The study team will use ANCOVA/mixed effects regression models to test the hypotheses. The investigative group has extensive experience with these analytic approaches in the analyses of longitudinal data after injury. These analytic approaches allow for the modeling of longitudinal data on patients, nested within trauma center sites (see also sample size and power discussion below for a more in-depth discussion of clustering). An important potential advantage of using longitudinal mixed models is the ability to use partial data on those of subjects with missing data, and therefore potentially ameliorate selection bias due to drop-out. In addition, mixed models naturally structure patient and center heterogeneity specifically allowing for random effects such as individual intercepts and slopes on time. Longitudinal regression models also allow the use of baseline covariates that may be prognostic or reflective of the study design.

Exploratory analyses will assess the impact of the intervention on primary and secondary outcomes for patients with and without pre-injury chronic medical conditions and with and without TBI. Exploratory analyses will also assess for significant reductions in suicidal ideation, pain and drug use problems in intervention patients when compared to control patients. The study team will again use ANCOVA/mixed effects regression for these exploratory analyses.²⁹⁴⁻²⁹⁷ In order to assess for potential selection bias across clusters, demographic characteristics (e.g., gender, ethnicity, insurance status) will also be tested as main effects and interactions with treatment status.

3. Stepped wedge cluster randomized design

Variability in multiple trauma center characteristics can impact rates of recruitment (e.g., admission volumes, EHR capacity), rates of PTSD (e.g., percentages of patients with violent injury admissions, intensive care unit admission rates), and the ability to follow patients longitudinally (e.g., patient demographic characteristics such as being homeless, clinical characteristics such as substance use problems). The study team initially considered using a stratified randomization procedure; however given the potential variability in multiple trauma center characteristics the study team will use a stepped wedge cluster randomized design for the UH3

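### Model C's global test of no intervention effect includes β8, the baseline difference, so it also tests baseline balance

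*Combined protocol and SAP*

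**What the plan says.** Under heading 3 of the Statistical Analysis Plan (stepped wedge cluster randomized design), Model C is a repeated-measures model. Its outcome "denotes patient outcome at follow up time i (i=1,2,3,4) (baseline, 3m, 6m, 12m"), so the baseline score is an outcome (i=1). It is not a covariate, as it is in Model A. Follow-up indicators exist only for i=2, 3 and 4 (β5 to β7). Condition enters as a main effect, β8, and in interactions with the three indicators, β9 to β11.

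Two hypotheses are attached to the model:

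- For the first, "the 12-month intervention effect would now be captured by the intervention-by-time interaction specific to the 12-month assessment time", that is, β11=0.
- For the other: "A second exploratory hypothesis would be the global null of no intervention effect at all follow-up times". It is written β8=β9=β10=β11=0, with a multivariate Wald test. The plan then explains: "Under this hypothesis the intervention and control means within a given period would be equivalent for all patient follow-up times".

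**The concern.** A contrast measured before treatment cannot be an intervention effect. The first hypothesis respects this and the global null does not, so two definitions of intervention effect stand side by side in the same section.

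What is at stake is the meaning of a significant result. Sites, not patients, are randomised. Under heading E (patient eligibility and recruitment), "Care manager subjects will then approach potential patient subjects about the study". Under Phase 6 of the study phases, the site is trained in the intervention first: "Following this training, each site begins recruitment of intervention patient subjects". The people who recruit therefore know which phase they are in. The plan recognises the risk and provides a check under heading 2 of the analysis plan: "In order to assess for potential selection bias across clusters, demographic characteristics" are to be tested as main effects and in interaction with treatment. If patients enrolled in the two phases differed systematically at baseline, the global test could reject although the intervention had done nothing, and the result would be reported under a label that says otherwise.

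**Working it through.** **What each coefficient means.** Within a period, intervention minus control in Model C is:

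- baseline: β8
- 3 months: β8+β9
- 6 months: β8+β10
- 12 months: β8+β11

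So β8=β9=β10=β11=0 is the intersection of two statements: equal baseline means (β8=0), and no difference in change from baseline (β9=β10=β11=0). If only the post-baseline means had been intended, the null would be β8+β9=β8+β10=β8+β11=0, which does not require β8=0 either.

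**Reproducing the plan's own figure.** The documents give no operating characteristics for the global test, so the design inputs were first checked against Table 10. Use the Hussey–Hughes variance with K=24 sites, T=5 periods, 6 sites per wave (24/4, assumed) and 6 patients per site-period (30 per site after attrition, over 5 periods). Then σ²=(1−ICC)/6, τ²=ICC, U=60, W=1080 and V=180:

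Var = Kσ²(σ²+Tτ²) / [(KU−W)σ² + (U²+KTU−TW−KV)τ²]

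At ICC 0.02: 24×0.1633×(0.1633+0.1) / (360×0.1633 + 1080×0.02) = 1.0323/80.4 = 0.01284. Multiply by the baseline-adjustment factor 1−0.7²=0.51, take the square root (0.0809), and multiply by 1.960+0.842=2.802. The result is 0.227. The four ICCs give 0.216, 0.220, 0.227 and 0.231, which match Table 10.

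**Inputs for the global test.**

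- From Table 11: 40 patients per site (row "Cluster size at baseline"), hence 8 per site-period; 30 per site at 12 months, hence 6 per site-period; correlation 0.7; ICC 0.02; PTSD Checklist SD 15.
- Assumed: 85% and 80% retention at 3 and 6 months; compound symmetry with total variance 1 (site 0.02, patient 0.68, residual 0.30); Model C's random slopes set to zero; a 5% test level.
- Assumed baseline differences d: 0.1, 0.2 and 0.3 SD, or 1.5, 3 and 4.5 Checklist points.

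The information matrix of the Model C mean model gives SE(β8)=0.095 and SE(β11)=0.056. The rejection rate is P(χ²(df, λ) > critical value), with λ=(Lβ)ᵀ(LCLᵀ)⁻¹(Lβ), where C is the covariance matrix of the estimates and L picks out the tested coefficients. The critical values are 9.49 (4 df) and 7.81 (3 df). For d=0.2 persisting, β=(0.2,0,0,0), λ=4.87 on 4 df, and the rate is 0.386.

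Rejection rates when the intervention has no effect:

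| Pattern | Test | d=0.1 | d=0.2 | d=0.3 |
|---|---|---|---|---|
| d persists unchanged | 4 df | 12% | 39% | 76% |
| d persists unchanged | 3 df | 5% | 5% | 5% |
| d shrinks to 0.7 of its size | 4 df | 12% | 40% | 77.5% |
| d shrinks to 0.7 of its size | 3 df | 8% | 18% | 37% |
| d shrinks to 0.5 of its size | 4 df | 16% | 57% | 92% |
| d shrinks to 0.5 of its size | 3 df | 14% | 45% | 83% |

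For d=0.2 persisting, the 4-df rate runs from 43% at ICC 0.005 to 37% at ICC 0.03. Putting random slopes back changes it little: 36% or 33% with an assumed site-by-condition variance of 0.01 or 0.03, and 38% with an assumed patient-slope variance of 0.2 (time in years).

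**The case against.** The strongest reply is that the plan states what it tests. Its index list counts baseline as follow-up time i=1, and its explanatory sentence says the means are equal at all those times. Formula, index and explanation agree; only the words of the label do not. That is correct, and it makes this a mismatch of label and hypothesis rather than an algebraic slip. It does not rescue the label, because equal means at every visit including baseline is a different hypothesis from no intervention effect.

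Second, with unselective recruitment β8 is zero in expectation and the 4-df test keeps its 5% level. This stands. Every d above is assumed, and at 0.05 SD persisting the rate is only about 6.6%. The fixed entry rule (at least 3 risk domains, PTSD Checklist at least 35), the drift assessments and the trauma registry comparisons make a large difference less likely.

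Third, the 3-df test is fully protected only if the difference persists unchanged. This also stands, as the shrinkage rows show. Even so, it rejected less often than the 4-df test in every imbalance case in the table.

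Finally, nothing decisional rests on this test. That limits the weight of the point but does not remove it.

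**Conclusion.** The point holds, as a minor one. As written, the global null is a 4-df joint test of baseline balance and intervention effect under a label that names only the second. That follows from the model's algebra and needs no numerical assumption. The size of the consequence does: a false rejection requires a systematic enrolment difference, and the documents report none. The rates rest on the assumed d, the retention pattern, compound symmetry and the omitted random slopes. The primary Model A test of β6 adjusts for the baseline score and, like the β11 test, does not use this null.

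**What to change.** Restate the global null as β9=β10=β11=0 with a 3-df Wald test, keep β8 in the model, and report β8 with its confidence interval as a balance check.

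An alternative is to model the 3-, 6- and 12-month scores with the baseline score as a covariate, as Model A does, and test the three condition effects jointly. The plan should say which is chosen, because they protect against different patterns. The first holds 5% if a baseline difference persists unchanged. The second holds 5% if it regresses in line with the 0.7 correlation; if the difference persists unchanged, it rejects roughly 7%, 12% and 24% for d=0.1, 0.2 and 0.3. Those figures are approximate: the within-site slope, (0.7−0.02)/(1−0.02)=0.694, is treated as known.

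β8 should not be removed from the model to force equal baseline means, since that assumes the balance in doubt. With a persisting difference, the test of the three interactions would then reject 6%, 8% and 11%, and β11 would be biased by about 0.014 SD per 0.1 SD of imbalance.

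The cost is one line of wording and no new data. For a 0.15 SD effect at all three follow-ups and no baseline difference, power is 83% with either test. For 0.15 SD at 12 months only, it is 77% (3 df) against 73% (4 df). With the assumed patient-slope variance of 0.2, the last two become 66% and 61%, in the same order.
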